5. CONCOMITANT MEDICATIONS

Short-acting antacid agents may be taken, but it is recommended that these not be taken from 2 hours before to 2 hours after dosing of ponatinib. Proton pump inhibitors may be administered concomitantly with ponatinib if felt to be in the patient's best interest.

Patients currently taking drugs that are generally accepted to have a risk of causing Torsades de Pointes (including: quinidine, procainamide, disopyramide, amiodarone, sotalol, ibutilide, dofetilide, erythromycins, clarithromycin, chlorpromazine, haloperidol, mesoridazine, thioridazine, pimozide, cisapride, bepridil, droperidol, methadone, arsenic, chloroquine, domperidone, halofantrine, levomethadyl, pentamidine, sparfloxacin, lidoflazine) should change these to acceptable alternatives, if possible.

General guidelines regarding excluded and cautionary medications are summarized in Table 1 below.

Table 1. Excluded and Cautionary Medications

Excluded

Anticancer therapies including chemotherapy or other investigational therapy, including targeted small molecule agents: Excluded 5 half-lives prior to first dose and throughout venetoclax administration

Biologic agents (e.g., monoclonal antibodies) for anti-neoplastic intent: Excluded 30 days or 5 halflives (whichever is shorter) prior to first dose and throughout venetoclax administration. Rituximab given as part of this treatment protocol is an exception.

Grapefruit and grapefruit products

Seville Oranges (including marmalade containing Seville oranges)

Starfruit

Cautionary

Warfarin and coumarin derivatives

P-gp substrates

BCRP substrates

OATP1B1/1B3 substrates

P-gp inhibitors

BCRP inhibitors

Strong and Moderate CYP3A inhibitors

Strong and Moderate CYP3A inducers

Localized radiation is allowed if deemed in the best interest of the patient and after approval by the PI.

Drugs involving these enzymes and transporters can be found in the following webpage: http://medicine.iupui.edu/clinpharm/ddis/main-table/

6. STUDY PROCEDURES

6.1. Pre-Treatment Evaluation

- 1. History and physical examination, including height and weight, vital signs (blood pressure, respiratory rate, pulse and temperature) and ECOG performance status 2. Concomitant medication and medical history assessment within 24 hours of first dose
- 3. CBC with differential, electrolytes (potassium, calcium, magnesium, phosphorus), LDH, uric acid, creatinine, liver function tests (AST, ALT, total bilirubin), lipase, amylase, triglycerides, hepatitis B antibodies
- 4. Bone marrow aspirate, cytogenetics and PCR for BCR-ABL1. Quick Philadelphia screen (FISH) is acceptable.
- 5 ÈKG
- 6. Pregnancy test in female patients of appropriate age and menopausal state within 1 week of first dose
- 7. Echocardiogram or MUGA scan to assess cardiac function
- 8. Biomarker studies including CyTOF, BH3 profiling, and next-generation targeted sequencing and SNP array (performed on bone marrow and peripheral blood)

All pretreatment evaluation must be performed within 2 weeks of first dose of the study drug, unless otherwise specified as above.

6.2 Evaluation During Study

- History and physical examination, including vital signs (blood pressure, respiratory rate, pulse and temperature) and ECOG performance status prior to each cycle
- 2. Evaluation for toxicity assessment prior to each cycle
- 3. Assessment of concomitant medications prior to each cycle.
- 4. CBC with differential 1-2 times weekly for cycle 1, then prior to each subsequent cycle
- In addition to TLS monitoring during the venetoclax ramp-up period (section 4.6), electrolytes (potassium, calcium, magnesium, phosphorus), LDH, uric acid, creatinine, liver function tests (AST, ALT, total bilirubin) at least weekly for cycle 1, then prior to each subsequent cycle
- 6. Amylase and lipase as clinically indicated (e.g. for patients with abdominal pain)
- 7. Bone marrow aspiration to be performed cycle 1 on day 7 (± 2 days) in patients without recent ponatinib exposure only but must be prior to the initiation of venetoclax, and again at day 28 (± 5 days) for patients with recent ponatinib exposure or day 35 (± 5 days) for patients without recent ponatinib exposure but must be prior to the beginning of cycle 2. Additional bone marrow assessment every 2-3 cycles or as clinically indicated. Cytogenetics (unless previously diploid) and PCR for BCR-ABL1 should be sent with each bone marrow evaluation.
- 8. EKG at baseline, during cycle 3, then every 3 months
- 9. Echocardiogram or MUGÁ during cycle 4 and then every 3 months, and as clinically indicated
- 10. Biomarker studies including CyTOF (on day 7 ± 2 days of cycle 1 for patients without recent ponatinib exposure only, at the end of cycle 1 and at the time of relapse), BH3 profiling (on day 7 ± 2 days of cycle 1 for patients without recent ponatinib exposure only, at the time of relapse). Relapse samples will be collected from bone marrow and peripheral blood.

Failure to collect biomarker studies at any time point due to logistical reasons will not be considered a protocol deviation or violation.

A study visit is a visit to MD Anderson Cancer Center every course.

	Pre	Cycle 1	Cycle 2	Cycle 3	Cycle 4	Cycles 5+	Follow- Up
Informed consent	Х						
History + physical	Х	X	X	X	X	X Every cycle	
Vital signs	X	X	X	X	X	X Every cycle	
Performance Status	X						
Concomitant medication assessment ⁵	Х	Х	Х	Х	X	X Every cycle	Х
Toxicity (AE) assessment		Х	Х	Х	Х	X Every cycle	Х
CBC with diff	Х	X	X	X	X	X Every cycle	
Electrolytes (potassium, calcium, magnesium, phosphorus), LDH, uric acid, creatinine, liver function tests (AST, ALT, total bilirubin), lipase and amylase ⁴	X	X	х	х	х	X Every cycle	
Triglycerides	Χ						

Hepatitis B antibodies	Χ						
Bone marrow aspirate	Χ	X ¹	X			X ²	
Pregnancy test (If indicated)	Χ						
EKG	Χ			Х		X Every 3 months	
Echocardiogram or MUGA	Х				Х	X Every 3 months	
CyTOF ⁶	Χ	X 3					
BH3 profiling ⁶	Χ	X 3					
Next-generation sequencing and SNP array ⁶	Х						
Survival status and subsequent treatment							Х

¹Bone marrow aspiration on day 7 (±1 days) for patients without recent ponatinib exposure only and at end of cycle 1 (day 28 [±5 days] for patients with recent ponatinib exposure and day 35 [±5 days] for patients without recent ponatinib exposure).

6.3 Follow-up

Thirty days after last dose of the study drugs concomitant medication and AE assessment will be recorded. This may be done over the phone with a member of the study staff.

Patients discontinued from study treatment for any reason other than withdrawal of consent for treatment will continue to be assessed for survival. Survival information (i.e. the date and cause of death) and subsequent treatment will be collected via telephone calls and/or clinical visits every 6 months (+/- 2 months) until death or withdrawal of consent.

7. EFFICACY AND SAFETY ASSESSMENTS

7.1. CRITERIA FOR RESPONSE

- Complete Remission (CR): Normalization of the peripheral blood and bone marrow with 5% or less blasts in normocellular or hypercellular marrow with a granulocyte count of 1 x 10⁹/L or above, and platelet count of 100 x 10⁹/L. Complete resolution of all sites of extramedullary disease is required for CR.
- Complete remission without recovery of counts (CRi): Peripheral blood and marrow results as for CR, but with incomplete recover of counts (platelets < 100 x 10⁹/L; neutrophils < 1 x 10⁹/L).
- 3. Complete cytogenetic response (CCyR): Same as for CR with cytogenetics showing diploid karyotype (valid only for patients with abnormal cytogenetics at enrollment)

²After achieving CR/CRi, bone marrow should be performed every 2-3 cycles or as clinically indicated.

³In patients without recent ponatinib exposure, BH3 profiling will be assessed on days 1 and 7 of cycle 1, CyTOF will be assessed on days 1, 7 and 35 of cycle 1. In patients with recent ponatinib exposure, BH3 profiling will be assessed on day 1 of cycle 1, CyTOF will be assessed on days 1 and 28 of cycle

^{1.} CyTOF and BH3 profiling will also be performed at the time of relapse.

4Amylase and lipase will be checked in all patients at screening. Subsequent amylase and lipase only

need to be checked as clinically indicated (e.g. for patients with abdominal pain)

⁵ Concomitant medication data will not be entered into the case report form (Prometheus); however, concomitant medications will be documented in the subject's electronic medical record.

⁶ Biomarker studies will not be captured in the case report form.

- Complete molecular response (CMR): Same as for CR with RT-PCR for BCR-ABL <0.01% ²¹
- Major molecular response (MMR): Same as for CR with RT-PCR for BCR-ABL with 3 log reduction from baseline (for p190 transcripts) and/or ≤0.1% by the International Scale (for p210 transcripts)
- Partial Response (PR): As above for CR except for the presence of 6-25% marrow blasts
- 7. Progressive Disease (PD): increase of at least 25% in the absolute number of circulating or bone marrow blasts or development of extramedullary disease
- Relapse Disease: reappearance of blasts in the blood or bone marrow >5% or development of extramedullary disease after initial response.

7.2. EVALUATION OF TOXICITY

- Toxicities will be graded according to the NCI Common Toxicity Criteria for Adverse Event Reporting Version 4.0. The toxicity of the regimen will be monitored continuously during the course of the study.
- 2. AEs will be recorded in the subject's source documents from the first dose through 30 days after the last dose. Serious Adverse Events (SAEs) will be captured from the time of the first protocol-specific intervention. The Principal Investigator will sign and date the Adverse Event Record (AE logs) per patient after the completion of each course. Following signature, the AE logs will be used as source documentation for the adverse events for attribution.

7.3. CRITERIA TO STOP TREATMENT

- Failure to achieve CR/CRi after 2 cycles of treatment, unless the patient is deemed to be deriving clinical benefit (e.g. blast reduction not meeting criteria for CR/CRi) as assessed by the treating physician and PI
- 2. Unacceptable toxicity judged to be related to therapy by the investigator, as defined by the NCI Common Toxicity Criteria (irreversible or prolonged (> 42 days) grade 4 hematological toxicity or grade 4 non-hematological toxicity thought to be related to ponatinib or venetoclax), unless it has been been judged by the treating physician and PI that the patient is achieving clinical benefit.
- 3. Non-compliance by the patient with protocol requirements or patient's request to be removed from the study.
- Relapse, defined as >5% bone marrow blasts not attributed to hematopoietic recovery, occurring after initial response to therapy

Patients coming off treatment due to the above issues will continue to be followed for survival outcomes.

7.4 DEFINITION OF STUDY END-POINTS

- 1. Relapse-free survival is the time from documented CR/CRi until relapse or death.
- 2. Event-free survival is the time from the first day of treatment until any treatment failure (lack of response, relapse, or death).
- 3. Overall response rate is defined as the percentage of patients achieving CR or CRi
- **4. Overall survival** is defined as the time from the first day of treatment to time of death from any cause.

In the primary analysis, survival will not be censored for stem cell transplant.

8. REPORTING REQUIREMENTS

Adverse event reporting will be as per the NCI criteria and the MDACC Leukemia Specific Adverse Event Recording and Reporting Guidelines (Appendix C).

The descriptions and grading scales found in the revised NCI Common Terminology Criteria for Adverse Events (CTCAE) version 4.0 will be utilized for adverse event reporting. (http://ctep.cancer.gov/reporting/ctc.html).

These adverse events will be recorded in the Case Report Form (CRF):

- Any grade adverse event that is possibly, probably, or definitely related to the study drug(s)
- All serious adverse events regardless of attribution to the study drug(s)
- Any grade adverse event regardless of attribution to the study drugs(s) that results in any dose modification

Patients will be registered in CORe. Prometheus will be used for data entry and AE capture.

Baseline events will be recorded in the medical history section of the case report form (Prometheus) and will include the terminology event name, grade, and start date of the event. Abnormal laboratory values or test results will not be recorded or reported as adverse events unless it leads to therapeutic intervention, results in dose modification or interruption, or meets the protocol definition of a DLT or SAE.

AEs will be shared with AbbVie on an annual basis.

Serious Adverse Event Reporting (SAE) for M. D. Anderson-sponsored IND Protocols

An adverse event or suspected adverse reaction is considered "serious" if, in the view of either the investigator or the sponsor, it results in any of the following outcomes:

- Death
- A life-threatening adverse drug experience any adverse experience that places the
 patient, in the view of the initial reporter, at immediate risk of death from the adverse
 experience as it occurred. It does not include an adverse experience that, had it occurred
 in a more severe form, might have caused death.
- Inpatient hospitalization (with the exception of planned hospitalization period for cycle 1) or prolongation of existing hospitalization
- A persistent or significant incapacity or substantial disruption of the ability to conduct normal life functions.
- A congenital anomaly/birth defect.

Important medical events that may not result in death, be life-threatening, or require hospitalization may be considered a serious adverse drug experience when, based upon appropriate medical judgment, they may jeopardize the patient or subject and may require medical or surgical intervention to prevent one of the outcomes listed in this definition. Examples of such medical events include allergic bronchospasm requiring intensive treatment in an emergency room or at home, blood dyscrasias or convulsions that do not result in inpatient hospitalization, or the development of drug dependency or drug abuse (21 CFR 312.32).

Important medical events as defined above, may also be considered serious adverse
events. Any important medical event can and should be reported as an SAE if deemed
appropriate by the Principal Investigator or the IND Sponsor, IND Office.

All events occurring during the conduct of a protocol and meeting the definition of a SAE must be reported to the IRB in accordance with the timeframes and procedures outlined in "The University of Texas M. D. Anderson Cancer Center Institutional Review Board Policy for Investigators on Reporting Unanticipated Adverse Events for Drugs and Devices". Unless stated otherwise in the protocol, all SAEs, expected or unexpected, must be reported to the IND Office, regardless of attribution (within 5 working days of knowledge of the event).

- All life-threatening or fatal events, that are unexpected, and related to the study drug, must
 have a written report submitted within 24 hours (next working day) of knowledge of the event
 to the Safety Project Manager in the IND Office.
- Unless otherwise noted, the electronic SAE application (eSAE) will be utilized for safety reporting to the IND Office and MDACC IRB.
- Serious adverse events will be captured from the time of the first protocol-specific
 intervention, until 30 days after the last dose of drug, unless the participant withdraws
 consent. Serious adverse events must be followed until clinical recovery is complete and
 laboratory tests have returned to baseline, progression of the event has stabilized, or there
 has been acceptable resolution of the event.
- Additionally, any serious adverse events that occur after the 30 day time period that are
 related to the study treatment must be reported to the IND Office. This may include the
 development of a secondary malignancy.

Adverse event reporting will be as per the NCI criteria and the MDACC Leukemia Specific Adverse Event Recording and Reporting Guidelines, located in protocol appendix A.

- An adverse event is the appearance or worsening of any undesirable sign, symptom, or
 medical condition occurring after starting the study drug even if the event is not considered to
 be related to study drug. Medical conditions/diseases present before starting study drug are
 only considered adverse events if they worsen after starting study drug. Abnormal laboratory
 values or test results constitute adverse events only if they induce clinical signs or symptoms,
 are considered clinically significant, or require therapy.
- The investigator (or physician designee) is responsible for verifying and providing source documentation for all adverse events and assigning the attribution for all adverse events for subjects enrolled.

Reporting to FDA:

• Serious adverse events will be forwarded to FDA by the IND Sponsor (Safety Project Manager IND Office) according to 21 CFR 312.32.

It is the responsibility of the PI and the research team to ensure serious adverse events are reported according to the Code of Federal Regulations, Good Clinical Practices, the protocol guidelines, the sponsor's guidelines, and Institutional Review Board policy.

Reporting to Abbvie:

Product Complaints: In addition to compliance with all FDA requirements pursuant to 21 CFR 211 and 21 CFR 820, Principal Investigator will report to AbbVie within 24 hours any suspected quality defect in an AbbVie Product or its AbbVie-provided packaging, labeling, or medical device component (collectively, "Product Complaint"). Principal Investigator will report Product Complaints that involve an AbbVie Product, whether AbbVie has supplied the AbbVie Product used in the Study or not. AbbVie's contact for reporting Product Complaints shall be [contact]

In addition to compliance with all FDA reporting requirements pursuant to 21 C.F.R. § 312, the PI shall:

- report to AbbVie all serious adverse events experienced by a study subject receiving an AbbVie
 product within 24 hours of learning of the event regardless of the relationship of the event to the
 AbbVie product. Principal Investigator shall make available to AbbVie promptly such records as
 may be necessary and pertinent to investigate any such event, if specifically requested by
 AbbVie; and in addition, report all non-serious adverse events of tumor lysis syndrome for
 studies involving ABT-199
- copy AbbVie on the submission to the FDA of events meeting the definition of IND safety reports at the time of submission to the Agency; and
- notify AbbVie upon any subject receiving an AbbVie Product who becomes pregnant

AbbVie's contact for reporting serious adverse drug experiences, pregnancy experiences, nonserious adverse events of tumor lysis syndrome, and communication of FDA submissions of IND safety reports shall be [contact]

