- If any laboratory changes are noted in cycle 1, and deemed clinically significant for TLS by the investigator, no additional venetoclax doses should be administered until resolution. TLS prophylaxis may need to be continued with subsequent cycles based on the ongoing risk of development of TLS.
- Drug interruption for up to 48 hours following transient chemical changes and laboratory TLS may be allowed and will not require a dose reduction. If the TLS has not resolved within 48 hours, then the dose should be reduced.
- 4.7 Completion of Phase I The phase I portion will define the DLTs, MTD and RP2D of
 the combination treatment. Dose escalation will proceed in standard '3+3' design (see
 Statistical Methods section). Once the MTD is established (or if the MTD is not reached with
 800 mg of venetoclax), the phase II portion of the study will commence.

• 4.8 Definition of DLT -

A DLT will be defined as any of the following adverse events that cannot be considered primarily related to the underlying malignancy, or a comorbid condition, occurring:

- For patients without recent ponatinib exposure, between day 8 and day 35 of cycle 1 (with the exception of hematologic toxicity which may be assessed up to day 49 of cycle 1)
- For patients with recent ponatinib exposure, between day 1 and day 28 of cycle 1 (with the exception of hematologic toxicity which may be assessed up to day 42 of cycle 1)

Any ≥ grade 3 non-hematologic toxicity with the following exceptions:

- Grade 3 alopecia
- Grade 3 nausea, vomiting, diarrhea with electrolyte abnormalities lasting less than 48
 hours that are not clinically significant and that does not require total parenteral
 nutrition (TPN), tube-feeding, or hospitalization
- Infection, unless the infection resulted from unexpectedly complicated by the degree
 or duration of myelosuppression in the absence of persistent leukemia.

Patients who receive at least a full course of therapy will be considered to be evaluable for toxicity/DLT and will not be replaced unless the PI determines that further additional patients at that dose level are required for safety purposes.

Hematologic toxicity will be defined as:

- For patients without recent ponatinib exposure, failure to recover ANC > 500/μL or platelet count > 25,000/μL by day 49.
- For patients with recent ponatinib exposure, failure to recover ANC > 500/µL or platelet count > 25,000/µL by day 42.

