- Phase II: A efficacy/toxicity summary must be submitted after the first 6 evaluable patients complete the second cycle of study treatment, and every 2 patients thereafter.

A copy of the cohort summary should be placed in the Investigator's Regulatory Binder under "sponsor correspondence".

Analysis Plan: Demographic/clinical characteristics and safety data of the patients will be summarized using descriptive statistics such as mean, standard deviation, median and range.

For the primary efficacy analysis, we will estimate the OR for the combination treatment (defined as the proportion of patients achieving CR or CRi after 2 cycles of treatment), along with the 95% credible interval. This regimen will be considered worthy of further investigation if an OR rate of at least 60% is achieved. Patients who drop out of the study before completing 2 cycles will be treated as "failures" for the primary analysis. The association between response and patient's clinical characteristics such as apoptotic protein expression, will be examined by Wilcoxon's rank sum test or Fisher's exact test, as appropriate.

The proportion of patient achieving CMR (as assessed by PCR for BCR-ABL transcripts) after 2 cycles of therapy will be estimated. The proportion of patients proceeding to ASCT and median time to ASCT will also be reported.

Kaplan-Meier curves will be used to estimate unadjusted OS and RFS distributions. Overall survival defined as the time from treatment initiation to death or last follow-up. RFS is defined as the time from the date of remission to relapse from CR or death from any cause whichever occurs first. Median OS and RFS as well as 1-year OS and RFS rates will be reported. Comparisons of time-to-event endpoints by important subgroups will be made using the log-rank tests.

Patients who enrolled in the phase I part of the trial who receive the MTD of venetoclax will be included in all efficacy analyses.

Toxicity type, severity and attribution will be summarized for each patient using frequency tables.

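### The section 8 list for CRF entry can miss a clinical DLT, and leaves non-serious grade 3 or higher events judged unrelated out of the safety tables unless they change a dose

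*Combined protocol and SAP*

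**What the plan says.** Section 8 (Reporting Requirements) names three classes of event for the CRF:

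- The first rests on a link to treatment: "Any grade adverse event that is possibly, probably, or definitely related to the study drug(s".
- The second takes every SAE, whatever its presumed cause.
- The third rests on a change of dose: "Any grade adverse event regardless of attribution to the study drugs(s) that results in any dose modification".

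No item names DLTs, and none names severe events irrespective of cause. A separate sentence in section 8 keeps abnormal laboratory values and test results out of adverse event recording unless they prompt treatment, change or interrupt a dose, or satisfy a further clause: "or meets the protocol definition of a DLT or SAE".

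Section 4.8 (Definition of DLT) counts events in the cycle 1 window that "cannot be considered primarily related to the underlying malignancy, or a comorbid condition". Non-hematologic events qualify from grade 3 upwards, with exceptions for alopecia, some gastrointestinal events and most infections. Hematologic DLTs are failures of neutrophil or platelet recovery by a fixed day. Attribution to study drug is not a condition.

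Section 7.2 has a wider net at source: "AEs will be recorded in the subject's source documents from the first dose through 30 days after the last dose", with adverse event logs signed by the principal investigator after each course. The analysis plan in section 10 then promises: "Toxicity type, severity and attribution will be summarized for each patient using frequency tables".

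**The concern.** The two tests ask different questions. For a non-serious event that changes no dose, the CRF list asks whether study drug might be a cause. The DLT definition asks whether leukemia or a comorbid condition is the main cause. An event with a third cause passes the DLT test and fails the CRF test.

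Safety is a secondary objective (section 2.2). The trial is open label with one arm, so attribution is a judgement made by people who know the treatment. If the database holds unrelated events only when they are serious or alter a dose, the attribution tables are truncated on one side. A reader of those tables cannot then see how many severe events were set aside, or test whether the conclusions depend on that judgement.

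**Working it through.** **1. What a DLT must be to escape the CRF.** Setting section 4.8 against the section 8 list, all four conditions must hold:

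- It is clinical. Laboratory and test findings that meet the DLT definition are recorded under the laboratory sentence, which covers the hematologic DLTs.
- It is not serious. Section 8 counts as serious any prolongation of a hospital stay, and important medical events if so judged.
- It is judged not even possibly related to study drug, yet not primarily due to leukemia or comorbidity.
- It leads to no dose modification.

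**2. Whether such an event can arise.** It can. Cycle 1 includes intrathecal methotrexate and cytarabine, optional rituximab (section 4.3) and suggested anti-infectives (section 4.4). Section 8 does not define study drug, and section 7.3 names only ponatinib and venetoclax when it describes treatment-related toxicity. A grade 3 headache ascribed to an intrathecal injection is neither leukemia nor comorbidity and is not among the section 4.8 exceptions. If it is non-serious and changes no dose, it meets section 4.8 and matches no item on the CRF list. The seriousness route is also narrower early in the DLT window, because the planned cycle 1 admission is exempt from the SAE definition.

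**3. The safety tables.** This part does not depend on the DLT definition. Any clinical grade 3 or higher event, in any cycle, that is non-serious, judged unrelated and changes no dose is off the list. Section 8 names Prometheus for data entry and adverse event capture. Tables built from it would show unrelated events only where they were serious or altered a dose.

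**4. The 3+3 figure.** The only stated figure that depends on the DLT count is the escalation table in section 10. The rule escalates on 0 of 3, or on 1 of 3 followed by 0 of 3:

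P(escalate) = (1 − p)³ + 3p(1 − p)² × (1 − p)³

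For p = 0.1 to 0.9 this gives 0.906, 0.709, 0.494, 0.309, 0.172, 0.082, 0.032, 0.009 and 0.001. All nine agree with the printed values.

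Suppose a share m of DLTs did not reach the dose decision. The effective rate is then p(1 − m). The documents give no value for m, so a range is shown:

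| True DLT rate | m = 0 | m = 5% | m = 10% | m = 20% |
|---|---|---|---|---|
| 30% | 0.494 | 0.525 | 0.557 | 0.622 |
| 40% | 0.309 | 0.343 | 0.378 | 0.454 |

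For example, at 30% with m = 10%, p = 0.27 and 0.73³ + 3 × 0.27 × 0.73⁵ = 0.389 + 0.168 = 0.557.

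**5. The phase II toxicity rule.** Table 2 counts drug-related grade 4-5 events. The first item on the CRF list takes related events of any grade, so the filter removes nothing from this count.

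**The case against.** The strongest reply is that the CRF is not the only record. Section 7.2 puts adverse events in source documents with no attribution filter. Section 8 requires attribution for every adverse event and sends all SAEs to the IND office whatever their cause. Section 10 requires a phase I toxicity summary after every 3 evaluable patients, and IND office approval before a dose level changes. An event absent from the CRF need not be absent from the 3+3 count. This stands, with one limit: the protocol does not say what the summary contains or which record it draws on.

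A second reply is that an event of unclear cause, not primarily due to leukemia or comorbidity, will often be rated possibly related and so be entered. That also stands, and it is why the DLT gap is narrow.

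Third, the leukemia-specific recording guideline, cited as Appendix C in one place and Appendix A in another, is not in the text available here and may add recording rules. Even so, section 8 states its own list, and anyone following that list would leave these events out.

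Some stronger readings are tempting but unsupported:

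- A reader might infer that DLTs are in fact being lost. The documents show only that one could be.
- A reader might infer that escalation is materially too easy. If one third of DLTs were missed, 30% would become 0.30 × 2/3 = 20%, and the plan's table would move from 0.49 to 0.71. Nothing supports that share, and dose decisions are not stated to rest on the CRF.
- A reader might infer that the incidence of severe events from any cause cannot be recovered. It cannot be computed from the CRF, but the events remain in source.

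**Conclusion.** The mismatch is real, and its consequence is limited. Followed as written, section 8 leaves out of the CRF a narrow class of clinical DLTs and, more broadly, non-serious non-laboratory grade 3 or higher events that are judged unrelated and change no dose. The certain effect is on the section 10 safety tables, assuming they are built from the CRF: they would be incomplete for unrelated events, by an amount the documents do not allow one to estimate. Hematologic and other laboratory DLTs are covered, and the phase II toxicity boundary is untouched. The escalation figures are illustrative and apply only if dose decisions used CRF data alone. The change is worth making because it is cheap and makes the safety results less dependent on unblinded attribution.

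**What to change.** Add two items to the section 8 CRF list: *any event meeting the section 4.8 DLT definition*, and *all grade 3 or higher non-laboratory adverse events regardless of attribution*. Keep the existing laboratory-value filter, since section 4.5 notes that cytopenias are common in this population and lifting the filter would add many entries. In section 10, tabulate these events regardless of attribution beside the drug-related ones. If the recording guideline in the appendix already requires this, section 8 should say so, and its appendix letter should be made consistent.

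The cost is modest extra data entry from source documents that section 7.2 already requires. At full accrual this covers about 26 to 32 patients: up to 26 at the phase II dose, plus at most 12 − 6 = 6 phase I patients treated at another level. The toxicity table will also look less favourable.
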